10.3 Methods and Timing for Capturing and Assessing Safety Parameters

10.3.1 Adverse Event Reporting Period

The study AE reporting period is as follows:

- After informed consent but prior to initiation of study drug, only SAEs associated with any protocol-imposed interventions will be collected. AEs occurring during this time period should be recorded on the Medical History eCRF.
- After informed consent is obtained and following infusion of study drug, the reporting period for all non-serious AEs and SAEs begins and continues for approximately 5 years or until study discontinuation/termination, whichever is longer.

The criteria for determining, and the reporting of SAEs is provided in Section 10.2.

10.3.2 Eliciting Adverse Events

Care will be taken not to introduce bias when detecting AEs and/or SAEs. Open-ended and non-leading verbal questioning of the subject is the preferred method to inquire about AE occurrences. The Investigator will record all relevant AE/SAE/EOSI information in the subject's medical record and AE Case Report Form (eCRF).

10.3.3 Assessment of Seriousness, Severity, and Causality

The Investigator responsible for the care of the subject or medically qualified designee will assess AEs for severity, relationship to study drug, and seriousness (refer to Section 10.2 for SAE definitions). These assessments must be made by a study clinician with the training and

authority to make a diagnosis (eg, MD/DO, physician's assistant, nurse practitioner, or DDS).

10.3.3.1 Seriousness

The Investigator will assess if an AE should be classified as "serious" based on the seriousness criteria enumerated in Section 10.2. Seriousness serves as a guide for defining regulatory reporting obligations.

10.3.3.2 Severity

Severity (as in mild, moderate, or severe headache) is not equivalent to seriousness, which is based on subject/event outcome or action criteria usually associated with events that pose a threat to a subject's life or functioning. The Investigator will determine the severity of each AE, SAE and EOSI using the NCI CTCAE v4.03. Adverse events that do not have a corresponding CTCAE term will be assessed according to the general guidelines for grading used in the CTCAE v4.03 as stated in Table 10.3.3.2.1.

Table 10.3.3.2.1: Adverse Event Grading (Severity) Scale

Grade	Description	
1	Mild: asymptomatic or mild symptoms; clinical or diagnostic observation indicated	ons only; intervention not
2	Moderate: minimal, local or noninvasive intervention indicated; limiting age appropriate instrumental activities of daily living (ADL) ^a	
3	Severe or medically significant but not immediately life-threatening: hospitalization or prolongation of hospitalization indicated; disabling; limiting self-care ADL ^b	
4	Life threatening consequences; urgent intervention indicated	Grade 4 and 5 AEs
5	Death related to AE	should always be reported as SAEs

^a Instrumental ADL refer to the following examples: preparing meals, shopping for groceries or clothes, using the telephone, managing money.

10.3.3.3 Causality

The Investigator will determine the relationship of an AE to the study drug and/or corticosteroids and/or other immunosuppressant agents and will record it on the source documents and AE eCRF. To ensure consistency of causality assessments, Investigators should apply the guidance in Table 10.3.3.3.1.

^b Self-care ADL refer to the following examples: bathing, dressing and undressing, feeding oneself, using the toilet , taking medications, not bedridden.

Table 10.3.3.3.1: Causality Attribution Guidance

Relationship	Description
Not Related	 Exposure to the IP and/or corticosteroids and/or other immunosuppressant agents has not occurred OR
	The administration of the IP and/or corticosteroids and/or other immunosuppressant agents and the occurrence of the AE are not reasonably related in time
	OR
	 The AE is considered likely to be related to an etiology other than the use of the IP and/or corticosteroids and/or other immunosuppressant agents; that is, there are no facts, evidence, or arguments to suggest a causal relationship to the IP and/or corticosteroids and/or other immunosuppressant agents.
Related	The administration of the IP and/or corticosteroids and/or other immunosuppressant agents and the occurrence of the AE are reasonably related in time AND
	The AE could not possibly be explained by factors or causes other than exposure to the IP and/or corticosteroids and/or other immunosuppressant agents
	OR
	The administration of IP and/or corticosteroids and/or other immunosuppressant agents and the occurrence of the AE are reasonably related in time
	AND
	 The AE is more likely explained by exposure to the IP and/or corticosteroids and/or other immunosuppressant agents than by other factors or causes

Factors suggestive of a causal relationship could include (but are not limited to):

- Plausible temporal relationship
- Absence of alternative explanations
- Rarity of event in a given patient or disease state
- Absence of event prior to study drug and/or corticosteroid and/or other immunosuppressant agent exposure

- Consistency with study product pharmacology
- Known relationship to underlying mechanism of study drug and/or corticosteroid and/or other immunosuppressant agent action
- Similarity to adverse reactions seen with related drug products
- Abatement of AE with discontinuation of study drug and/or corticosteroids and/or other immunosuppressant agents, and/or recurrence of AE with reintroduction of study drug and/or corticosteroids and/or other immunosuppressant agents

The Investigator's assessment of causality for individual AE reports is part of the study documentation process. Regardless of the Investigator's assessment of causality for individual AE reports, the Sponsor will promptly evaluate all reported SAEs against cumulative product experience to identify and expeditiously communicate possible new safety findings to Investigators and applicable regulatory authorities.

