"A pharmaceutical form of an active ingredient or placebo being tested or used as a reference in a clinical trial, including a product with a marketing authorization when used or assembled (formulated or packaged) in a way different from the approved form, or when used for an unapproved indication, or when used to gain further information about an approved use" (from International Conference on Harmonisation of Technical Requirements for Registration of Pharmaceuticals for Human Use ICH Harmonised Tripartite Guideline: Guideline for Good Clinical Practice E6 [ICH E6 (R2)]).

The terms "IP" and "study drug" may be used interchangeably in the protocol.

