9.3.3.1 Study Safety Evaluation Criteria

If any of the following events occur in a subject in the study who has received BMN 270 infusion, an urgent evaluation by the DMC will be required and further enrollment into the trial will be temporarily put on hold if recommended by the DMC per Section 9.1.

- 1. Liver dysfunction (criteria do not apply to ALT elevations with an extra-hepatic etiology):
 - ALT > 5x ULN, for more than 2 weeks
 - o ALT > 3x ULN and (total bilirubin > 2x ULN or INR > 1.5)
 - ALT > 3x ULN with signs and symptoms of liver dysfunction
- 2. The occurrence of Grade 4 or Grade 5 adverse events assessed as related to study drug (events of liver dysfunction are defined above).
- 3. The occurrence of an AE of hepatic failure.
- 4. The detection of high-titer neutralizing antibodies (>5 BU) to hFVIII following BMN 270 infusion in two subjects.
- 5. The occurrence of any cancer (except non-melanoma skin cancer) at any point after BMN 270 infusion.
- 6. The occurrence of a thromboembolic event with FVIII activity > 150 IU/dL in one subject.

If any of the following events occurs in a subject in the study who has received BMN 270 infusion, an urgent evaluation by the DMC will be required. Further enrollment into the trial will continue while DMC evaluation is ongoing, unless deemed otherwise by the DMC:

- 1. The detection of high-titer neutralizing antibodies (>5 BU) to hFVIII following BMN 270 infusion in one subject.
- 2. Occurrence of a thromboembolic event in one subject.
- 9.3.4 Subject Identification and Replacement of Subjects

Each subject will be assigned a unique subject identifier. This unique identifier will be on all eCRF pages. In legal jurisdictions where use of initials is not permitted, a substitute identifier will be used.

Subjects who withdraw from the study after receiving BMN 270 will not be replaced.

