14.7 Safety Analysis

The Medical Dictionary for Regulatory Activities terminology (MedDRA) will be used by the Sponsor to assign system organ class and preferred term classification to events and diseases, based on the original terms entered on the eCRF.

All AEs will be coded using the current version of MedDRA. The incidence of AEs will be summarized by system organ class, preferred term, relationship to study drug, and severity.

A by-subject listing will be provided for those subjects who experience a serious AE (SAE), including death, or experience an AE associated with early withdrawal from the study or study drug.

Clinical laboratory data will be summarized by the type of laboratory test. For each clinical laboratory test, descriptive statistics will be provided on Baseline as well as all subsequent visits. Descriptive statistics for physical examination results and vital signs will also be provided.

Detailed statistical methods will be provided in the SAP.

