The incidence of AEs will be summarized by system organ class, preferred term, relationship to study drug, seriousness, and severity. A by-subject listing will be provided for subjects who experience a SAE, including death, or experience an AE associated with early withdrawal from the study. Clinical laboratory test values, vital signs, vector shedding and immune response parameters will be summarized descriptively by visit.

Additional details on the primary analysis of the key efficacy and safety endpoints, as well as the planned supportive, sensitivity, and subgroup analyses and analyses for the other endpoints will be provided in the 2-year analysis SAP.

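### The causality table rates BMN 270, corticosteroids and other immunosuppressants as one pooled exposure, but the AE summaries and a DMC criterion need relationship to BMN 270 alone

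*Protocol*

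**What the plan says.** Section 10.3.3.3 (Causality) opens with the task: "The Investigator will determine the relationship of an AE to the study drug and/or corticosteroids and/or other immunosuppressant agents". Table 10.3.3.3.1 then gives the only guidance for doing it, with two outcomes. *Related* can be reached when the timing fits and "The AE is more likely explained by exposure to the IP and/or corticosteroids and/or other immunosuppressant agents than by other factors or causes". *Not Related* has three routes: no exposure to the listed agents, timing that does not fit, or "The AE is considered likely to be related to an etiology other than the use of the IP and/or corticosteroids and/or other immunosuppressant agents". The wording is the same in the Amendment 6 and the United States-specific Amendment 7 text, so it is not an artefact of extraction.

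Elsewhere the quantity is narrower. Section 10.3.3 has the investigator "assess AEs for severity, relationship to study drug, and seriousness". Section 14.7 plans that "The incidence of AEs will be summarized by system organ class, preferred term, relationship to study drug, and severity", and Section 25.3.6 says the same for the 2-year analysis: "The incidence of AEs will be summarized by system organ class, preferred term, relationship to study drug, seriousness, and severity". One criterion for urgent DMC evaluation in Section 9.3.3.1 is "The occurrence of Grade 4 or Grade 5 adverse events assessed as related to study drug". Section 4 fixes the meaning of the term: "The terms 'IP' and 'study drug' may be used interchangeably in the protocol".

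**The concern.** The rating that the table produces is not the quantity that the analyses and the DMC criterion call for. The table answers whether any of three exposures explains the event. The summaries and the criterion ask whether BMN 270 does.

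The difference matters in this trial because corticosteroid exposure is built into its conduct. Section 7.4 reports ALT elevation in most subjects given BMN 270 and mentions unwanted effects of high-dose or prolonged corticosteroids. The course in Section 9.4.8.2 and Table 9.1.6 runs 2 + 3 + 1 + 1 + 1 = 8 weeks. Section 9.4.8.2 foresees specific corticosteroid complications and sends AEs suspected to come from these agents through the same Section 10. With a single arm, no concurrent group would show which events belong to the corticosteroid course. Attribution is made at the site, so if only one combined rating is collected, an analysis plan cannot separate it later without going back to the sites.

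**Working it through.** No sample size, power or error rate is involved, so the check is one of text and logic: take a reaction caused only by corticosteroids, with no reason to suspect BMN 270, put it through the table, then follow the result to where it is used.

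1. *Related*, timing condition. The event follows exposure to a listed agent within a reasonable time. Met, through the corticosteroid.
2. *Related*, explanation condition. A listed agent explains the event better than anything outside the list. Met, again through the corticosteroid. With step 1, the rating is *Related*.
3. *Not Related*, no exposure. Fails: the subject has received both BMN 270 and a corticosteroid.
4. *Not Related*, timing. Fails, for the reason in step 1.
5. *Not Related*, other etiology. Fails: the corticosteroid is inside the set of agents that an alternative cause must lie outside.

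So the literal rating is *Related*, and no route leads to *Not Related*.

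Downstream uses, side by side:

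| Place | Quantity named | What the table supplies, read literally |
|---|---|---|
| 10.3.3 | relationship to study drug | relationship to any of three agents |
| 14.7 | AE incidence by relationship to study drug | the same pooled rating |
| 25.3.6 | AE incidence by relationship to study drug | the same pooled rating |
| 9.3.3.1, criterion 2 | Grade 4 or 5 AE related to study drug | the same pooled rating |

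Section 4 makes study drug and IP the same thing, and the table lists corticosteroids alongside the IP as a separate item. Study drug therefore cannot be read as including corticosteroids, and the left and right columns differ.

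One concrete path: Section 10.4.1.4 requires a Grade 4 laboratory abnormality to be recorded as an SAE. If corticosteroids caused it, the table rates it *Related*. If that rating is the only one held, it reads as meeting criterion 2 of Section 9.3.3.1.

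**The case against.** The strongest reply is that no miscount has been shown. The eCRF is not among the documents, and it may already hold one relationship field per agent. The lead sentence of 10.3.3.3 can be read agent by agent. That reading gives the no-exposure route to *Not Related* a purpose: a subject never given corticosteroids is unrelated to them. Under the pooled reading that route does almost no work, because Section 10.3.1 starts collection of non-serious AEs only after infusion. Every downstream place names study drug alone, which suggests that a study-drug-specific rating was intended.

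Much of this stands. Separate fields would probably avoid the miscount in practice, so a reader who infers that results are already mixed goes further than the documents allow. What does not fall away is the text. No section says that the table is applied per agent, and even with separate fields its wording would not let a corticosteroid cause count as another etiology in the BMN 270 field.

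The consequences are also narrower than they might seem:

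- **Enrollment hold.** A reader might infer that a corticosteroid reaction could stop enrollment. Section 25.3.2 places the last dosing about two years before November 2021, so under Amendment 7 the hold is moot. An extra urgent DMC evaluation remains possible, and it would err toward caution.
- **Expedited reporting.** Site reporting of SAEs and EOSI under Section 10.5.1 does not depend on relatedness and is unaffected.
- **Inference.** The safety analysis in Section 25.3.6 is descriptive, so no test or error rate is touched.

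**Conclusion.** The point holds as a conflict between a stated rule and the quantity it is meant to supply. Table 10.3.3.3.1, read literally, misclassifies corticosteroid-only reactions for every use that asks about relationship to BMN 270. Whether this reaches the results depends on the eCRF. If it holds a single relationship field, the study-drug-related incidence would include corticosteroid reactions, and the Grade 4 or 5 criterion could be met by one.

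The size cannot be derived from the documents. A reader might want to put a percentage on it. Supposing that 60-90% of about 130 subjects receive corticosteroids and that 20-50% of those have an AE attributed to them gives 0.60 × 0.20 = 12% to 0.90 × 0.50 = 45%, or about 16 to 59 subjects. Neither share appears in the protocol, so this range is not a finding. It also counts subjects with such an AE, not the change in the study-drug-related rate. ALT elevation is an EOSI recorded as an AE and is described as expected after this type of therapy, so many of the same subjects may already carry a related AE. The overall subject-level rate may therefore move little, and any distortion would show mainly for individual preferred terms typical of corticosteroids.

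This is worth correcting because relationship to study drug is one of the ways the safety results are to be presented. It does not bear on the efficacy inference.

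**What to change.** Three changes of wording:

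- In Table 10.3.3.3.1, replace the pooled list with *the agent being assessed*, so that each other agent counts as an alternative etiology.
- In Section 10.3.3.3, state that attribution is made and recorded separately for BMN 270, corticosteroids and other immunosuppressants.
- In Sections 9.3.3.1, 14.7 and 25.3.6, state that related to study drug means the BMN 270 attribution only.

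If the eCRF already has a field per agent, the cost is limited to this text and matching wording in the analysis plan. If not, it needs added fields, and AEs already recorded in subjects who received corticosteroids or other immunosuppressants need queries. That work grows as follow-up continues toward 5 years.

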10.4 Procedures for Recording Adverse Events

10.4.1 Recording Adverse Events on an eCRF

Investigators should use precise medical terminology when recording AEs or SAEs on the AE eCRF. Avoid colloquialisms and abbreviations.

Record only one diagnosis, sign, or symptom per event field on the AE eCRF (eg, nausea and vomiting should not be recorded in the same entry, but as 2 separate entries).

In order to classify AEs and diseases, preferred terms will be assigned by the Sponsor to the original terms entered on the AE eCRF, using MedDRA (Medical Dictionary for Regulatory Activities) terminology.

10.4.1.1 Diagnosis versus Signs and Symptoms

The Investigator will attempt to establish a diagnosis of the event based on signs, symptoms, and/or other clinical information. Whenever possible, the diagnosis (not the individual signs/symptoms) will be documented as the AE/SAE. Using accepted medical terminology, enter the diagnosis (if known). If not known, enter sign(s) and/or symptom(s). If a diagnosis subsequently becomes available, then this diagnosis should be entered on the AE (or SAE, as appropriate) eCRF, replacing the original entries where appropriate.

10.4.1.2 Adverse Events Occurring Secondary to Other Events

In general, AEs occurring secondary to other events (eg, cascade events) should be identified by their primary cause. For example, if severe diarrhea is known to have resulted in dehydration, it is sufficient to record only diarrhea as an AE or SAE on the AE eCRF.

However, medically important events that may be linked and/or separated in time should be

recorded as independent events on the AE eCRF. For example, if severe hemorrhage leads to renal failure, both events should be recorded separately on the AE eCRF.

10.4.1.3 Persistent or Recurrent Adverse Events

A persistent AE (duration of adverse event > 7 days) is one that extends continuously, without resolution, between subject evaluation time points. Events that change in severity necessitate the recording of an additional AE. AEs that do not have a change in severity should be recorded only once on the eCRF.

A recurrent AE is one that occurs and resolves between subject evaluation time points, but then subsequently recurs. All recurrences of the AE should be recorded on the AE eCRF. For example, if a subject has an adverse event of ALT increased that subsequently resolves, but the subject's ALT increases again, that should be reported as two adverse events – the initial ALT increase, and the second ALT increase.

10.4.1.4 Abnormal Laboratory Values

Laboratory test results will be recorded on the laboratory results pages of the eCRF, or appear on electronically produced laboratory reports submitted directly from the central laboratory, if applicable.

Any laboratory result abnormality fulfilling the criteria for a SAE or EOSI should be reported as such, and recorded in the AE eCRF.

Any laboratory result abnormality of CTCAE Grade 4 or 5 should be recorded as an SAE in the AE eCRF.

A clinical laboratory abnormality is considered clinically significant and should be documented as an AE if not refuted by a repeat test to confirm the abnormality and **any** one or more of the following conditions is met:

- Accompanied by clinical symptoms
- Requiring a change in concomitant therapy (eg, addition of, interruption of, discontinuation of, or any other change in a concomitant medication, therapy or treatment).
- The abnormality suggests a disease and/or organ toxicity
- The abnormality is of a degree that requires active management (eg, change of dose, discontinuation of study drug, more frequent follow-up assessments, further diagnostic investigation, etc.)

This applies to any protocol and non-protocol specified safety and efficacy laboratory result from tests performed after the first dose of study medication that falls outside the laboratory reference range and meets the clinical significance criteria.

This does not apply to any abnormal laboratory result that falls outside the laboratory reference range but that does not meet the clinical significance criteria (these will be analyzed and reported as laboratory abnormalities), those that are considered AEs of the type explicitly exempted by the protocol, or those which are a result of an AE that has already been reported.

For purposes of this study, laboratory tests showing a decreased level of FVIII activity should not be reported as adverse events unless there is an impact to clinical outcomes (eg, increased rate of bleeding, worsening of joint disease).

10.4.1.5 Pre-existing Conditions

A pre-existing condition is one that is present prior to administration of BMN 270. Such conditions should be recorded as medical history on the appropriate eCRF.

A pre-existing condition should be recorded as an AE or SAE during the study only if the frequency, intensity, or character of the condition worsens during the study period. It is important to convey the concept that a pre-existing condition has changed by including applicable language in the verbatim description of the event (eg, more frequent headaches).

10.4.1.6 General Physical Examination Findings

At screening, any clinically significant abnormality should be recorded as a pre-existing condition (refer to Section 10.4.1.5). During the study, any new clinically significant findings and/or abnormalities discovered on physical examination that meet the definition of an AE (or an SAE) must be recorded and documented as an AE or SAE on the AE eCRF.

